16.5 Data Analysis

Demographic and clinical characteristics of the sample, as well as response, toxicity by grade and loss to follow up will be summarized using descriptive statistics. Incidence of grade 3 or higher acute toxicities (overall and gastrointestinal), incidence of organ preservation will be calculated. Descriptive statistics from the FACT-C questionnaire will be generated for evaluation of anorectal function at 1 year. The incidence of post radiotherapy grade 3 or higher toxicities at 1 year will also be provided.

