2.2 Secondary Objectives

1. To obtain prospective patient reported outcomes from an organ preservation approach for early stage rectal cancer.
2. To determine the incidence of any grade ≥ 3 toxicity during treatment.
3. To determine the incidence of post chemoradiotherapy grade ≥ 3 toxicity at 1 year
4. To determine quality of anorectal function at 1 year using the FACT-C questionnaire.

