16 STATISTICAL CONSIDERATIONS

16.1 Study Objectives and Endpoints

Primary Objective:

Demonstrate that sequential short course radiotherapy followed by 8 cycles of multi-drug chemotherapy will elicit a rate of significant clinical response to allow an organ preservation approach for at least 30% (6/20) patients at 1 year.

Secondary Objectives

1. Obtain prospective patient reported outcomes from an organ preservation approach for early stage rectal cancer.
2. Determine the incidence of any grade ≥ 3 toxicity during treatment.
3. Determine the incidence of post chemoradiotherapy grade ≥ 3 toxicity at 1 year
4. Determine quality of anorectal function at 1 year by FACT-C

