Please circle or mark one number per line to indicate your response as it applies to the past 7 days.

	ADDITIONAL CONCERNS	Not at all	A little bit	Some- what	Quite a bit	Very much
C1	I have swelling or cramps in my stomach area	0	1	2	3	4
C2	I am losing weight	0	1	2	3	4
C3	I have control of my bowels	0	1	2	3	4
C4	I can digest my food well	0	1	2	3	4
C5	I have diarrhea (diarrhoea)	0	1	2	3	4
C6	I have a good appetite	0	1	2	3	4
C7	I like the appearance of my body	0	1	2	3	4
Q2	Do you have an ostomy appliance? (Mark one box)	 No	or	 Yes		
	If yes, please answer the next two items:					
C8	I am embarrassed by my ostomy appliance	0	1	2	3	4
C9	Caring for my ostomy appliance is difficult	0	1	2	3	4

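### Section 16.5 evaluates anorectal function at 1 year from unspecified FACT-C descriptive statistics, although only two, arguably three, of the 34 items put to every patient concern bowel function

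*Combined protocol and SAP*

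**What the plan says.** Section 2.2 lists general patient-reported outcomes as secondary objective 1 and, separately, as objective 4, "To determine quality of anorectal function at 1 year using the FACT-C questionnaire". Section 16.1 repeats it: "Determine quality of anorectal function at 1 year by FACT-C". No other instrument is named for this purpose.

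The analysis is one sentence in Section 16.5: "Descriptive statistics from the FACT-C questionnaire will be generated for evaluation of anorectal function at 1 year". It does not say whether the statistics are for the total, the subscales or single items. It gives no scoring rule, no comparison with baseline and no handling of patients with an ostomy.

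FACT-C is collected before treatment (Sections 5.1, 11 and 12), after chemotherapy (Section 5.3) and at about 1 year (Section 5.4). The form in Appendix A has four general well-being sections and an additional-concerns section. Question Q2 on the form asks about an ostomy appliance, and two further items follow for patients who have one.

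**The concern.** The objective is specific and the instrument is mostly general. The item that speaks most directly to it is C3, "I have control of my bowels". Most of the others ask about energy, mood, family support, work, appetite, body image and similar matters. A summary at total or category level could stay flat while continence worsens, and stable general well-being could then be reported as anorectal function.

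Such a reading has a precedent. Section 1 describes the institution's earlier phase II trial, where mean FACT-C category scores were 20.6 before treatment, 20.2 before surgery and 20.0 after surgery (p = 0.8). That lack of change was taken as confirming an absence of treatment-related toxicity.

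Function also belongs to this trial's rationale: Section 1 gives poorer rectal function after low anterior resection as a drawback of standard surgery. In addition, a 1-year value alone cannot separate dysfunction present before treatment from change that came later. And C3 does not measure anorectal function in a patient who has an ostomy.

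**Working it through.** The plan states no target, precision or effect size for this objective, so there is no figure of its own to reproduce. The check is a count of items in Appendix A and their share of the possible score.

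**Inputs (Appendix A).** Physical 7, social/family 7, emotional 6, functional 7, additional concerns 7, ostomy items 2. Each is scored 0 to 4.

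**Item count.** 7 + 7 + 6 + 7 + 7 = 34 items put to every patient (one, on sex life, may be declined). With the ostomy items, 36.

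**Which items concern bowel function.** C3 (bowel control) and C5 (diarrhea) do so directly. C1, "I have swelling or cramps in my stomach area", is borderline. C4, "I can digest my food well", is about digestion and counts only on the loosest reading. C8 and C9 concern embarrassment about the appliance and its care. No item asks separately about urgency, stool frequency, incomplete evacuation or leakage.

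**Assumption.** The documents give no scoring rule. I use a simple sum of 0-4 items, all turned to the same direction (C3 is worded favourably, C1 and C5 unfavourably).

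**Maximum scores.** All 34 items: 34 × 4 = 136. Additional-concerns section without the ostomy items: 7 × 4 = 28.

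| Items counted | Points | Share of 136 | Share of 28 |
|---|---|---|---|
| C3 | 4 | 2.9% | 14% |
| C3 + C5 | 8 | 5.9% | 29% |
| C3 + C5 + C1 | 12 | 8.8% | 43% |
| C3 + C5 + C1 + C4 | 16 | 11.8% | 57% |

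A patient who moved from best to worst on both C3 and C5 would change a total by 8 of 136 points. On the strict count, even the most relevant section takes 20 of its 28 points (71%) from other items. The other four sections contain neither item.

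**Baseline.** Sections 5.1, 11 and 12 all collect the form before treatment. The sentence in Section 16.5 refers only to 1 year.

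**Ostomy status.** Section 5.3 recommends extirpative surgery for some patients with residual disease, with treatment continuing off-study. Neither Section 5.4 nor Section 16.5 says whether these patients contribute 1-year forms or how they would be shown. The earlier trial's 1-year functional well-being was 13.2 with an ostomy and 19.2 without (Section 1), so the mix of patients could matter.

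**The case against.** The strongest reply is that the plan does not commit itself to total or category scores. Item-level summaries of C3 and C5 are descriptive statistics from FACT-C and fit the sentence as written. This stands. A reader might infer that the objective cannot be answered; the documents do not support that, because the relevant items are collected and give a partial answer. The defect is that the plan leaves open which summary counts.

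A reader might also infer that patients with and without an ostomy will be pooled. The plan does not say so. The form records ostomy status, and the earlier trial reported a FACT-C result by ostomy status.

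On baseline, the objective asks for function at 1 year and the analysis matches it literally. Nothing bars a paired summary under objective 1. That is fair, but the plan promises none.

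A precision argument is tempting too: take the earlier trial's SD of about 5.4, obtain a 95% half-width of about 2.5 points at n = 20, and conclude that a 2-point loss of bowel control would be hidden. This fails, because it sets a shift on one 0-4 item against the SD of a category score. For C3 itself the largest possible SD at n = 20 is √(20 × 2² / 19) = 2.05, so the half-width is at most 2.09 × 2.05 / √20 = 0.96. For paired change, which runs from -4 to 4, the limit is 1.92. A 2-point mean shift lies outside both.

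Finally, no test or claim of preserved function is planned, and grade 3 and above adverse events are collected to 1 year (Section 9.6), which is a partial backstop for severe harm. This limits the consequence but does not supply the missing definition.

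**Conclusion.** The point holds as a gap in the analysis plan. Section 16.5 does not say which FACT-C items or scores represent anorectal function, and only C3 and C5, arguably C1, do. Total or category summaries would mostly describe general well-being: the two direct items are 5.9% of the total and 29% of the additional-concerns section. The shares rest on an assumed simple sum; the item count does not. The baseline form is collected but not used for this objective.

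Even item-level reporting covers continence and diarrhea only, not anorectal function as a whole. The objective is secondary and descriptive, in a pilot of 20 evaluable patients, and the go/no-go rule in Section 16.2 depends only on organ preservation. The change is worth making because it costs almost nothing and prevents the choice of summary from being made after the data are seen.

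**What to change.** In Section 16.5:

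- Name C3 and C5 as the items reported for objective 4, with C1 as support, and state the direction of scoring.
- Report the 1-year distribution of each item and the paired change from baseline in patients without an ostomy (Q2 = No), with the number of pairs.
- Show patients with an ostomy separately, and say whether patients treated off-study after surgery contribute 1-year forms.
- Report FACT-C totals and subscales under objective 1.
- Describe the objective 4 result as limited to continence and diarrhea.

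The 1-year window should also be reconciled, so that paired change refers to one time point: Section 5.4 counts 10-14 months from the start of radiotherapy, Section 11 counts from radiotherapy and Section 12 from chemoradiation.

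The cost is analysis wording only. The items, the baseline form and the ostomy question are already collected. The price is a more modest claim.

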7 CHEMOTHERAPY GUIDELINES

7.1 Chemotherapy Schedule and Doses

Chemotherapy should begin 2 to 4 weeks after completion of radiotherapy and will consist of 5FU/leucovorin/oxaliplatin every other week for 8 courses (16 weeks). Alternatively, capecitabine/oxaliplatin (CAPE PO 1000 mg/m² BID days 1-14 Q21 days, oxaliplatin IV 130 mg/m² IV Q21 days on day 1) x 5 cycles over 15 weeks may be administered instead of FOLFOX. A maximum (total) delay of treatment of 4 weeks is allowed per protocol due to factors/AEs listed in this section. Cumulative delays in excess of 4 weeks will need to be discussed with the Principal Investigator. Such cases will need to be individualized depending on the clinical scenario.

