9.1 Definitions

9.1.1 Adverse Events (AEs)

Definition: any unfavorable medical occurrence in a human subject including any abnormal sign, symptom, or disease.

Grading: the descriptions and grading scales found in the revised NCI Common Terminology Criteria for Adverse Events (CTCAE) version 4.0 will be utilized for all toxicity reporting. A copy of the CTCAE version 4.0 can be downloaded from the CTEP website.

Attribution (relatedness), Expectedness, and Seriousness: the definitions for the terms listed that should be used are those provided by the Department of Health and Human Services' Office for Human Research Protections (OHRP). A copy of this guidance can be found on OHRP's website:

<http://www.hhs.gov/ohrp/policy/AdvEvtGuid.html>

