9.6 Timeframe for Reporting Required Events

All Grade 3 and above adverse events should be collected until 1 year post start of radiation therapy on case report forms and reported to the QASMC as part of the DSM Report as applicable.

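### Section 16.5 starts the late-toxicity window after radiotherapy, but the objective starts it after chemoradiotherapy, so the reported figure could include all chemotherapy toxicity

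*Combined protocol and SAP*

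**What the plan says.** Secondary objective 3 reads, in Section 2.2, "To determine the incidence of post chemoradiotherapy grade ≥ 3 toxicity at 1 year". The list of objectives at the front of the protocol and Section 16.1 use the same anchor. Objective 2 is separate: "Determine the incidence of any grade ≥ 3 toxicity during treatment".

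Section 16.5 is the only place that says how these will be analysed. For the first year it says "The incidence of post radiotherapy grade 3 or higher toxicities at 1 year will also be provided". For the early period it says "Incidence of grade 3 or higher acute toxicities (overall and gastrointestinal), incidence of organ preservation will be calculated". It gives no start or end date for either period.

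Treatment is sequential. Section 7.1 says "Chemotherapy should begin 2 to 4 weeks after completion of radiotherapy". On collection, Section 9.6 says "All Grade 3 and above adverse events should be collected until 1 year post start of radiation therapy", and the study calendar in Section 11 uses the same limit.

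**The concern.** If chemotherapy were given together with radiation, *post radiotherapy* and *post chemoradiotherapy* would mean much the same. Here radiotherapy is over within two weeks and every dose of chemotherapy comes later. A grade 3 neutropenia in the third cycle is toxicity during treatment, and it is also post radiotherapy. It is not post chemoradiotherapy.

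The analysis sentence therefore does not match the objective it serves. Taken literally, it overlaps objective 2 and leaves objective 3 without an analysis of its own. Section 1 argues that the side-effect profile of radiation and chemotherapy may allow better overall quality of life when the rectum is preserved. What toxicity appears once treatment has ended bears directly on that argument. A figure that mixes chemotherapy toxicity with later toxicity would not show it.

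**Working it through.** **Inputs**

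- Radiotherapy: five once-daily fractions, up to 10 business days allowed (Section 6.1), so 1 to 2 weeks.
- Gap to chemotherapy: 2 to 4 weeks (Section 7.1).
- Chemotherapy: FOLFOX, 8 courses every 14 days, or CapeOx, 5 cycles of 21 days (Section 7.1).
- Allowed total delay: 0 to 4 weeks (Section 7.1). Longer delays go to the principal investigator and are not modelled.
- End of collection: 1 year from the start of radiotherapy, taken as week 52 (Section 9.6).

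**Plan's own durations.** 8 × 14 / 7 = 16 weeks and 5 × 21 / 7 = 15 weeks. Both agree with Section 7.1. With delay, chemotherapy occupies 15 to 15 + 4 = 19 weeks (CapeOx) or 16 to 16 + 4 = 20 weeks (FOLFOX), so 15 to 20 weeks overall.

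**Timeline in weeks from the start of radiotherapy**

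End of chemotherapy = radiotherapy + gap + chemotherapy + delay. Share before chemotherapy ends = (end of chemotherapy − end of radiotherapy) / (52 − end of radiotherapy).

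| Case | End of chemotherapy | Post-radiotherapy window | Share before chemotherapy ends | Weeks left to week 52 |
|---|---|---|---|---|
| Shortest CapeOx | 1 + 2 + 15 = 18 | 51 | 17/51 = 33% | 34 |
| Shortest FOLFOX | 1 + 2 + 16 = 19 | 51 | 18/51 = 35% | 33 |
| Longest CapeOx | 2 + 4 + 15 + 4 = 25 | 50 | 23/50 = 46% | 27 |
| Longest FOLFOX | 2 + 4 + 16 + 4 = 26 | 50 | 24/50 = 48% | 26 |

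Without the gap, chemotherapy alone takes 15/51 = 29% to 20/50 = 40% of the post-radiotherapy window.

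**Effect on the reported incidence.** The documents give no grade 3 or higher rates for this regimen, so these are assumptions: a proportion *c* of 10–50% of patients with an event during chemotherapy, a proportion *p* of 5–15% with an event after it, and independence between the two.

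Cumulative post-radiotherapy incidence = 1 − (1 − c)(1 − p).

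- Low end: 1 − 0.90 × 0.95 = 14.5%, or 2.9 of 20 patients, against 5% (1 of 20) post-chemotherapy.
- High end: 1 − 0.50 × 0.85 = 57.5%, or 11.5 of 20, against 15% (3 of 20).

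The excess is c(1 − p). It runs from 0.10 × 0.85 = 8.5 percentage points to 0.50 × 0.95 = 47.5 percentage points. The range is wide because the rates are unknown.

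**The case against.** The strongest defence is that *post radiotherapy* is loose wording. The same paragraph of Section 16.5 has a separate line for acute toxicities, which gives an acute and late split parallel to objectives 2 and 3. In addition, *at 1 year* could mean present at 1 year, and then a neutropenia that had resolved months earlier would not count.

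This stands in part. The milder reading is possible, so the documents support only that the figure could include chemotherapy toxicity, not that it must. They do not establish the milder reading either. *Acute* has no time limits, and nothing excludes an event on the acute line from the 1-year line. Section 16.5 speaks of incidence and describes no assessment at a fixed time point. The follow-up visit in Section 5.4 may fall at 10 to 14 months from the start of radiotherapy, while event collection closes at 12.

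A reader might also infer that the wording brings complications of later surgery into the count, since Section 9.1.1 defines an adverse event as "any unfavorable medical occurrence in a human subject including any abnormal sign, symptom, or disease". The documents do not support that inference. Under Section 5.3, surgery for residual disease follows restaging after chemotherapy, so it falls in either window and correcting the phrase would not remove it. Section 5.3 also has treatment proceed off-study at that point, and no section says whether later events count. That is a separate gap.

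Lastly, a reader might infer that a wrong toxicity rate would feed the phase II decision. The criterion in Section 16.2 and the stopping rule in Section 16.3 depend only on organ preservation.

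**Conclusion.** The mismatch is real and should be corrected. The stated analysis contradicts its own objective. On the plain cumulative reading, the Section 16.5 figure would take in the whole 15 to 20 weeks of chemotherapy, and the post-treatment period would be only the last 26 to 34 weeks of the year. These durations follow from the protocol's schedule with delay kept within the 4 weeks allowed.

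The figure would then overlap objective 2 and overstate post-treatment toxicity. The size of the overstatement cannot be fixed from the documents: the 14.5–57.5% against 5–15% rests on assumed rates, independence and the cumulative reading.

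The consequence is modest. It concerns a descriptive secondary safety result in a pilot of 20 evaluable patients. The primary endpoint, the stopping rule and the criterion for going on to phase II are unaffected.

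**What to change.** In Section 16.5:

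1. Replace *post radiotherapy* with *post chemoradiotherapy*. Define it as grade 3 or higher events with onset after the end of the last chemotherapy cycle given and up to 1 year from the start of radiotherapy, reported as cumulative incidence.
2. Define the acute, or during-treatment, period as the first radiotherapy fraction to the end of the last chemotherapy cycle given.
3. Assign each event to one period by its onset date.

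The cost is a wording change and one split of a table, with no extra patients or visits. Events of grade 3 and above are already collected to 1 year from the start of radiotherapy, and Section 12 has a chemotherapy form completed at the end of each cycle. Onset dates are assumed to be on the adverse event form, which the documents do not show. The small downside is that the late window is openly shown to be about 6 to 8 months (26 to 34 weeks), not a full year.

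Flagging events after off-study surgery on a separate line is optional. It depends on surgery dates being available, and Section 12 lists no surgery form.

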16.6 Accrual

Assuming 10% inevaluable cases, the overall accrual will be 22 patients. The rate of accrual for the study is expected to be about 8 patients per year. It is expected that the accrual period of the study will be completed in about 3 years.

17 MULTICENTER REGULATORY REQUIREMENTS

Washington University requires that each participating site sends its informed consent document to be reviewed and approved by the Washington University Regulatory Coordinator (or designee) prior to IRB/IEC submission.

Site activation is defined as when the secondary site has received official written documentation from the coordinating center that the site has been approved to begin enrollment. At a minimum, each participating institution must have the following documents on file at Washington University prior to study activation:

- Documentation of IRB approval of the study in the form of a letter or other official document from the participating institution's IRB. This documentation must show which version of the protocol was approved by the IRB.
- Documentation of IRB approval of an informed consent form. The consent must include a statement that data will be shared with Washington University, including the Quality Assurance and Safety Monitoring Committee (QASMC), the DSMC (if applicable), and the Washington University study team.

- Documentation of FWA, signed FDA Form 1572 (if applicable), and the CVs of all participating investigators.
- Protocol signature page signed and dated by the investigator at each participating site.

The coordinating center Principal Investigator (or designee) is responsible for disseminating to the participating sites all study updates, amendments, reportable adverse events, etc. Protocol/consent modifications and IB updates will be forwarded electronically to the secondary sites within 4 weeks of obtaining Washington University IRB approval. Activated secondary sites are expected to submit protocol/consent/IB modifications to their local IRBs within 4 weeks of receipt unless otherwise noted. Upon the secondary sites obtaining local IRB approval, documentation of such shall be sent to the Washington University study team within 2 weeks of receipt of approval.

Documentation of participating sites' IRB approval of annual continuing reviews, protocol amendments or revisions, all SAE reports, and all protocol violations/deviations/exceptions must be kept on file at Washington University.

The investigator or a designee from each institution must participate in a regular conference call to update and inform regarding the progress of the trial.

Appendix A: FACT-C Questionnaire

Patient ID#: _____

Date of Completion: _____

FACT-C (Version 4)

Below is a list of statements that other people with your illness have said are important. Please circle or mark one number per line to indicate your response as it applies to the past 7 days.

PHYSICAL WELL-BEING

		Not at all	A little bit	Some- what	Quite a bit	Very much
GP1	I have a lack of energy	0	1	2	3	4
GP2	I have nausea	0	1	2	3	4
GP3	Because of my physical condition, I have trouble meeting the needs of my family	0	1	2	3	4
GP4	I have pain	0	1	2	3	4
GP5	I am bothered by side effects of treatment	0	1	2	3	4
GP6	I feel ill	0	1	2	3	4
GP7	I am forced to spend time in bed	0	1	2	3	4

SOCIAL/FAMILY WELL-BEING

		Not at all	A little bit	Some- what	Quite a bit	Very much
GS1	I feel close to my friends	0	1	2	3	4
GS2	I get emotional support from my family	0	1	2	3	4
GS3	I get support from my friends	0	1	2	3	4
GS4	My family has accepted my illness	0	1	2	3	4
GS5	I am satisfied with family communication about my illness	0	1	2	3	4
GS6	I feel close to my partner (or the person who is my main support)	0	1	2	3	4
Q1	Regardless of your current level of sexual activity, please answer the following question. If you prefer not to answer it, please mark this box  and go to the next section.					
GS7	I am satisfied with my sex life	0	1	2	3	4

Patient ID#: _____

Date of Completion: _____

FACT-C (Version 4)

Please circle or mark one number per line to indicate your response as it applies to the past 7 days.

EMOTIONAL WELL-BEING		Not at all	A little bit	Some- what	Quite a bit	Very much
GE1	I feel sad	0	1	2	3	4
GE2	I am satisfied with how I am coping with my illness	0	1	2	3	4
GE3	I am losing hope in the fight against my illness	0	1	2	3	4
GE4	I feel nervous	0	1	2	3	4
GE5	I worry about dying	0	1	2	3	4
GE6	I worry that my condition will get worse	0	1	2	3	4

FUNCTIONAL WELL-BEING		Not at all	A little bit	Some- what	Quite a bit	Very much
GF1	I am able to work (include work at home)	0	1	2	3	4
GF2	My work (include work at home) is fulfilling	0	1	2	3	4
GF3	I am able to enjoy life	0	1	2	3	4
GF4	I have accepted my illness	0	1	2	3	4
GF5	I am sleeping well	0	1	2	3	4
GF6	I am enjoying the things I usually do for fun	0	1	2	3	4
GF7	I am content with the quality of my life right now	0	1	2	3	4

Patient ID#: _____

Date of Completion: _____

FACT-C (Version 4)

Please circle or mark one number per line to indicate your response as it applies to the past 7 days.

	ADDITIONAL CONCERNS	Not at all	A little bit	Some- what	Quite a bit	Very much
C1	I have swelling or cramps in my stomach area	0	1	2	3	4
C2	I am losing weight	0	1	2	3	4
C3	I have control of my bowels	0	1	2	3	4
C4	I can digest my food well	0	1	2	3	4
C5	I have diarrhea (diarrhoea)	0	1	2	3	4
C6	I have a good appetite	0	1	2	3	4
C7	I like the appearance of my body	0	1	2	3	4
Q2	Do you have an ostomy appliance? (Mark one box)	 No	or	 Yes		
	If yes, please answer the next two items:					
C8	I am embarrassed by my ostomy appliance	0	1	2	3	4
C9	Caring for my ostomy appliance is difficult	0	1	2	3	4
